Statistical Analysis	
SAFETY ANALYSIS
 
The reporting of safety data is descriptive (arithmetic mean, standard deviation (SD), coefficient of variation (CV), median, minimum, and maximum) will be calculated for quantitative safety data as well as for the difference from baseline, when appropriate.
 
The analysis will include all subjects who receive at least one dose of investigational product. The variables for safety endpoints are AEs, Local Application Site Reactions, vital signs measurements, clinical chemistry and hematology. AEs will be summarized based on the frequency of AEs and their severity for all treated subjects. All AEs will be coded using Medical Dictionary for Regulatory Activities (MedDRA) and summarized by treatment group. Data will be summarized using preferred term and primary system organ class, including verbatim term, dose level, severity, and relationship to treatment, will be provided.

	
Concomitant medications will be listed by treatment and coded using the most recent version of the World Health Organization (WHO) Drug Dictionary (DD).
 
EFFICACY ANALYSIS
 
The Evaluable Period for the outcome variables will be weeks 1, 4, 8 and 12. The superiority of the drug over the vehicle will be tested at week 8 based on the probability of improvement from baseline with a continuity-corrected Z-tests comparing the change from baseline of treatments vs Placebo. For all other evaluable periods, descriptive statistics for the change from baseline will be shown.
 
The change from baseline score of Skindex-16 will be compared among treatments at Week 12 using an ANOVA.

--	---

Table of Contents

Contents

STATISTICAL ANALYSIS PLAN REVIEW AND APPROVAL	2
PROTOCOL SYNOPSIS	3
1 LIST OF ABBREVIATION	14
2 INTRODUCTION	16
2.1 Study Overview	16
2.2 Study Flowchart	18
2.3 Schedule of Activities	19
3 STUDY OBJECTIVE AND ENDPOINTS	21
3.1 Study Objectives	21
3.1.1 Primary Objective.....	21
3.1.2 Exploratory Objectives.....	21
3.2 Study Endpoints	21
3.2.1 Safety & Tolerability (Primary).....	21
3.2.2 Efficacy (Exploratory).....	21
4 STUDY DESIGN.....	22
4.1 Summary of Study Design.....	22
4.2 Definition of Study Drugs.....	22
4.3 Sample Size Considerations	23
4.4 Study Withdrawal	23
4.5 Early Discontinuation	24
5 PLANNED ANALYSIS.....	24
5.1 Final Analysis.....	24
6 GENERAL CONSIDERATION FOR DATA ANALYSIS AND HANDLING.....	24
6.1 General Summary Table and Individual Subject Data Listing	24

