4 STUDY DESIGN

4.1 Summary of Study Design

This is a Prospective, Vehicle Controlled, Double Blind, Multicenter, Randomized Phase II trial, Comparing the effect of twice daily B244 application for 8 weeks vs. vehicle application on treatment of mild to moderate rosacea. We will enroll approximately 130 subjects and complete 104 subjects.

At Screening and Baseline, all subjects must have clinical diagnosis of mild to moderate rosacea and must have IGA score of 2-3 and CEA score of 2-3 to qualify for the study. After screening and recruitment, participants will be randomized to active or vehicle application for 8 weeks. Subjects will apply a total of 4 pumps of IP per application to the face twice-a-day. Randomization will be 1:1 B244 to Vehicle. Subjects will be provided with cleanser and moisturizer to use for the duration of the study. All B244 randomized subjects will be treated at the dose of 4×10^9 cells/ml via spray application. Screening will occur at Days -21 to -1. Washout will occur after Screening visit (Days -14 to -1) and randomization will occur during the baseline visit for the study (Day 1).

Efficacy will be assessed using Investigator Global Assessment (IGA) score, Clinician's Erythema Assessment (CEA) score, Patient Self-Assessment (PSA) score and patient reported Skindex 16. Clinical assessments of response to treatment will be made at Week 1 (Day 7), Week 4 (Day 28), and Week 8 (Day 56). At Baseline visit, subjects will receive a kit containing the drug product. Each bottle will be used for 2 weeks. At Week 4, subjects will return the used bottles from the kit and will be issued a new kit of drug product to be used from Week 4 through Week 8. Subjects will stop applying investigational product at Week 8 and will return investigational product at that visit. Subjects will come back for a 4-week post-treatment follow up visit at Week 12 (Day 84). Participant's safety will be monitored throughout the study. Safety will be assessed by monitoring reported adverse events, vital signs, clinical chemistry and hematology and overall tolerability of the investigational product.

Subjects would be required to discontinue the investigational product under the following circumstances:

- Development of an intercurrent illness that would jeopardize the safety, or significantly affect assessments of clinical status of a subject
- Either at the discretion of the Investigator or at the participant's request

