6.4 Data Presentation Conventions

Continuous variables (e.g. age) are summarized using descriptive statistics (the number of subjects with available data, the mean, standard deviation (SD), median, minimum and maximum). Categorical variables (e.g. race) are summarized using counts and percentages. Percentages are calculated using the total subjects per treatment group.

The following conventions are applied to all data presentations and summaries:

- For continuous variables, all mean and median values are formatted to one more decimal place than the measured value. Standard deviation values are formatted to two more decimal places than the measured value. Minimum and maximum values are presented with the same number of decimal places as the measured value.
- For categorical variables, the number and percentage of responses are presented in the form XX (XX.X %) where the percentage is in the parentheses.
- Date variables are formatted as DDMMMYYYY for presentation. Time is formatted in military time as HH:MM for presentation.
- Wherever possible, data will be decimal aligned.
- P-values, if applicable, will be presented to 4 decimal places. If the p-value is less than 0.0001 then it will be presented as <0.0001.

Unless otherwise stated, any statistical tests performed will use 2-sided tests at the 5% significance level.

The table and listing shells and table of contents as part of this SAP provide the expected layout and titles of the tables, listings and figures. Any changes to format, layout, titles, numbering, or any other minor deviation will not necessitate a revision to the SAP nor will it be considered a deviation from planned analyses. Only true differences in the analysis methods or data handling will necessitate such documentation. The appropriate listings supporting the tables will be included and are not specified in the individual sections throughout the document.

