6.5.4 Per-Protocol (PP) Population

The PP population includes all randomized subjects who met all inclusion/exclusion criteria, were compliant with the assigned study treatment, returned to the study site for the primary endpoint visit within the specified window (± 2 days) OR discontinued from the study as a treatment failure, and did not have any major protocol violations.

Subjects who administered at least 50 % of IP, have at least one baseline and post baseline in clinic visit and did not have any major protocol violations.

Subjects who discontinued early from the study due to lack of treatment effect after completing at least eight weeks of treatment should be included in the mITT and PP population as treatment failures and the change in IGA and CEA from the baseline visit to the last completed visit prior to discontinuation due to lack of efficacy should be carried forward in the primary endpoint analysis. Subjects discontinued early for other reasons should be excluded from the PP population but included in the mITT population.

The results in the mITT population will be considered definitive for superiority of each active treatment to vehicle with those in the PP population considered supportive. Safety analyses will be performed using the Safety population.

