8 STATISTICAL ANALYSES

8.1 Sample Size Determination

Sample size of 104 randomized 1:1 Active to Vehicle based on 80% power to detect 33% IGA response in Active group versus 10% in the Vehicle group, with two-sided test and $\alpha = 0.05$. Until mentioned all alpha value is set at 0.05.

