8.3 Efficacy Analysis

All efficacy endpoints are exploratory endpoints.

Assessment of Superiority:

- IGA treatment success, defined as “clear” or “almost clear” with a 2-grade improvement in IGA score from baseline to the end of treatment (Week 8).
- CEA treatment success, defined as “clear” or “almost clear” with a 2-grade improvement in CEA score from baseline to the end of treatment (Week 8).

Superiority will be based on the proportion of subjects for whom treatment was successful. The comparison will be through a continuity-corrected Z-tests. The Evaluable Period for the outcome variables will be weeks 1, 4, 8 and 12. The superiority of the drug over the vehicle will be tested at week 8 based on the probability of

improvement from baseline with a continuity-corrected Z-tests comparing the change from baseline of treatments vs Placebo. For all other evaluable periods, descriptive statistics for the change from baseline will be shown.

The null and alternative statistical hypotheses for the primary effectiveness endpoints are given by:

(*H*₀): The null hypothesis is that the probability of improving (baseline to week 8) with drug T (*Pr*_T) is less than or equal to the probability of improving with vehicle (*Pr*_V).

$$H_0: Pr_T - Pr_V \leq 0; Pr_T$$

(*H*_a): The alternative hypothesis is that the probability of improving with drug T (*Pr*_T) is greater than to the probability of improving with vehicle (*Pr*_V).

$$H_a: Pr_T > Pr_V; Pr_T - Pr_V > 0$$

For testing the superiority, the following SAS code will be used:

```
proc freq data = dataset;
  tables treat*outcome/riskdiff (equal);
run;
```

- Change of Skindex 16 patient reported outcome from Baseline to Week 1, Week 4, Week 8 and Week 12

The change from baseline score of Skindex-16 will be compared among treatments at Week 12 using an ANOVA, to test the Skindex 16 score change from Baseline to Week 12 for the two treatments. Also, descriptive stats will be used to assess the change from Baseline to Week 1, 4, 8 & 12.

- Change of IGA score at Baseline to Week 1, Week 4, Week 8 and Week 12.
- Change of CEA score at Baseline to Week 1, Week 4, Week 8 and Week 12.
- Change of PSA score at Baseline to Week 1, Week 4, Week 8 and Week 12.

Descriptive stats will be used to show the change from Baseline to Week 1, 4, 8 & 12.

- Supplemental Analysis

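### SAP v2 8.3 names a continuity-corrected Z-test for Week 8 superiority, but its code requests no correction, and 104 evaluable subjects reach the stated 80% power only without one

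*SAP*

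**What the plan says.** SAP v2 specifies the correction in words three times. Section 8.3 says of the treatment-success proportions: "The comparison will be through a continuity-corrected Z-tests". It repeats this for the Week 8 test of improvement from baseline, and the efficacy paragraph of the synopsis says the superiority test is done "with a continuity-corrected Z-tests comparing the change from baseline of treatments vs Placebo". Section 8.3 then gives the SAS code to be run for superiority. Its TABLES statement is "tables treat*outcome/riskdiff (equal" plus a closing bracket, so EQUAL is the only option. SAP v1 section 8.3 has the same test wording and the same code.

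Section 8.1 opens "Sample size of 104 randomized 1:1 Active to Vehicle" and claims 80% power for 33% versus 10% IGA response, two-sided, alpha 0.05. It names no test and mentions no correction. Protocol 14.2 carries the same statement. Section 4.1 shows that 104 means completers: "We will enroll approximately 130 subjects and complete 104 subjects". On sidedness, section 6.4 says: "Unless otherwise stated, any statistical tests performed will use 2-sided tests at the 5% significance level".

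**The concern.** Words and code describe the same test differently, and nothing ranks one above the other. Two analysts working faithfully from the SAP could put a borderline Week 8 result on opposite sides of 0.05, and the choice could be made after the data are seen. The variance estimate (pooled or unpooled) is also not stated, so the wording alone does not fix the test.

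The sample-size claim raises a separate question. With 52 evaluable subjects per arm the correction is not negligible, so a power figure that fits the uncorrected test need not fit the test the text names.

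The SAP places weight on this comparison. Section 6.5.4 says "The results in the mITT population will be considered definitive for superiority of each active treatment to vehicle", and section 8.1 sizes the trial on it.

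**Working it through.** **Inputs.** Response 0.33 versus 0.10, so d = 0.23; two-sided alpha 0.05; power 80% (SAP v2 8.1). 1:1 allocation, 20% dropout and about 130 enrolled (4.3). Missing values are not imputed in the main analysis (6.7.4), so the evaluable count, n = 52 per arm, drives power.

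**1. Reproduce the plan's own figures.** Dropout: 130 × 0.8 = 104, which agrees.

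Sample size with pooled null variance, mean rate 0.215:

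- Uncorrected: n = [1.96·√(2·0.215·0.785) + 0.8416·√(0.33·0.67 + 0.10·0.90)]² / 0.23² = 48.9, so 49 per arm, 98 in total.
- Corrected: n′ = (n/4)·[1 + √(1 + 4/(n·d))]² = 57.2, so 58 per arm, 116 in total.

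Unpooled variance gives 47 per arm (94) uncorrected and 55 per arm (110) corrected. None of these returns 104, so the formula behind it cannot be recovered. What can be checked is whether 104 delivers at least 80%.

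**2. Approximate power at 52 per arm.** SE₀ = √(2·0.215·0.785/52) = 0.0806; SE₁ = √((0.2211 + 0.09)/52) = 0.0773. The correction takes ½(1/52 + 1/52) = 1/52 = 0.0192 off the difference.

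- Pooled, uncorrected: (0.23 − 1.96·0.0806)/0.0773 = 0.932, power 82.4%.
- Pooled, corrected: (0.23 − 0.0192 − 1.96·0.0806)/0.0773 = 0.683, power 75.3%.
- Unpooled, uncorrected: 1.014, power 84.5%.
- Unpooled, corrected: 0.765, power 77.8%.

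**3. Exact values.** Enumerate all pairs of binomial counts and reject when |Z| ≥ 1.96:

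| Test | Power, 33% vs 10%, n = 52 | n per arm for 80% | Two-sided type I error at 10%/10% |
|---|---|---|---|
| Uncorrected, pooled | 84.0% | 47 | 4.9% |
| Uncorrected, unpooled (Wald) | 84.5% | 46 | 5.9% |
| Corrected, pooled | 76.3% | 56 | 1.9% |
| Corrected, unpooled | 78.0% | 54 | 2.4% |

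**4. How often the rules disagree at 0.05 under the planning rates.** Both unpooled, 6.5%; both pooled, 7.8%; pooled corrected against Wald, 8.2%.

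**5. A borderline example.** Take 13/52 versus 5/52, a difference of 8/52 = 0.1538.

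- Unpooled SE 0.0726: Z = 2.118, p = 0.034. Corrected: Z = (0.1538 − 0.0192)/0.0726 = 1.853, p = 0.064.
- Pooled SE 0.0742: Z = 2.074, p = 0.038. Corrected: Z = 1.814, p = 0.070.

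**6. Where the cut-offs fall.** With 4, 5 or 6 vehicle responders, Wald declares superiority from 11, 13 or 14 active responders. The corrected rule needs 13 with 4 vehicle responders, 14 with 5, and 15 (unpooled) or 16 (pooled) with 6.

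**The case against.** The strongest reply has four parts.

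- **The text/code conflict needs outside knowledge.** That RISKDIFF with EQUAL runs uncorrected is a property of the software, and the snippet, with its placeholder dataset name, could be read as a template subordinate to the text. This stands as a limit. It is visible in the documents that the code requests no correction, but the claim that two rules result rests on the default. The power shortfall does not depend on it.
- **Section 8.1 names no test and says only IGA response**, so no stated calculation is contradicted. It is true that 104 cannot be shown to come from an uncorrected formula. But every Week 8 superiority proportion in 8.3, whether treatment success or improvement, is assigned the corrected test, so the stated power is missed on either reading.
- **The shortfall is small**: 2.0 points unpooled, 3.7 pooled. The corrected test reaches 80% at 108 to 112 evaluable, which is 14% to 17% dropout from 130 instead of 20%. This is fair, and it is why the shortfall touches only the planning claim. A one-sided 5% test would also clear 80% with the correction, but 6.4 and 8.1 both say two-sided.
- **All efficacy endpoints are exploratory** (8.3), with no multiplicity control (protocol 14.3.5), and 6.5.4 can be read as ranking mITT above per-protocol. That lowers the stakes. It does not remove the need for a single rule for a formal test with stated hypotheses. At a common 10% rate the rules disagree less often, in about 3.0% to 4.1% of trials, and the correction can only remove significance.

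**Conclusion.** The point holds and should be fixed. The SAP's wording names a correction that its prescribed code does not request, and the test's variance is not stated. Assuming SAS applies no correction by default, one comparison has two decision rules, which differ in 6.5% to 8.2% of trials under the planning rates. If that assumption is wrong, text and code agree and only the power point remains.

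At 104 evaluable subjects, two-sided 0.05, the test named in the text has 76.3% to 78.0% exact power. The stated 80%, read as at least 80%, is met only without the correction. Only the text/code conflict can change a reported result. The primary objective, descriptive safety and tolerability, does not depend on this test.

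**What to change.** Before unblinding, name one test in 8.3 and the synopsis, including pooled or unpooled variance, and make the code match. Either option works:

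- **A. Drop the correction** and use the uncorrected pooled-variance Z-test (chi-square). Power at 104 evaluable is about 84%, with type I error about 4.9% at a common 10% rate. The code must then request that test; on the assumption above, the present line gives Wald, with 5.9%.
- **B. Keep the correction**, request it explicitly in the code, and restate power in 8.1 as about 76% (pooled) or 78% (unpooled) at 104 evaluable. This is the smaller departure from the existing text.

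Under either option, 8.1 should name the test its power refers to and describe 104 as evaluable subjects out of about 130 randomized with 20% dropout. Section 8.3 should say that the two-sided p-value of 6.4 governs, because its hypotheses are written one-sided.

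The cost is wording in 8.1, 8.3 and the synopsis and one line of code, with no additional patients.

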11.1.7 Clinician’s Erythema Assessment (CEA)

Clinician’s Erythema Assessment (CEA) will be will be evaluated at each study visit. The Investigator will assess the extent of rosacea based on the 5-point severity scale summarized below.

The Investigator will perform a static (“snap-shot”) evaluation of erythema severity using the CEA, and report the one integer that best describes the overall severity beginning from the Baseline Visit (Table 4). Although inflammation (papules, pustules, plaques) or dry appearance may obscure the level of erythema, underlying redness should be evaluated disregarding this effect. Inflammation or dry appearance may be noted, but perilesional erythema should not be included in this assessment. Transient erythema (flushing) will also not be included.

Table 4. Clinician Erythema Assessment

Score	Severity	Description
0	Clear	Clear skin with no signs of erythema
1	Almost clear	Almost clear, slight redness
2	Mild	Mild erythema; definite redness
3	Moderate	Moderate erythema; marked redness
4	Severe	Severe erythema; fiery redness

Questionnaire can be found in [Appendix 2](#).

11.1.8 Skindex 16

Skindex-16 instrument will be evaluated at each study visit. The participant will answer a questionnaire examining the relationship between the patient’s skin health and quality of life. Skindex16 questionnaire can be found in [Appendix 4](#).

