14.3.3 Hypothesis Testing/ Assessment of Efficacy

Further details of the planned statistical methods presented below will be provided in the study Statistical Analysis Plan (SAP). The purpose of the SAP is to further elaborate the statistical methods described in the protocol and describe analysis conventions to guide the statistical programming work. Any changes to the final SAP will be documented. Unless otherwise specified, the hypothesis testing will be conducted by the difference of means for a two-sample two-sided test with a significance level of 0.050.

The Evaluable Period for the outcome variables will be weeks 1, 4, 8 and 12. During each Evaluable Period an ordinal value based on IGA, CEA, PSA scores will be collected. The probability of improving will be the criteria to assess the superiority of the drug over the vehicle. The null and alternative statistical hypotheses for the primary effectiveness endpoints are given by:

(*H₀*) : The null hypothesis is that the probability of improving (across the scale) with drug T (*Pr_T*) is less than or equal to the probability of improving with vehicle (*Pr_V*)

$$H_0: PrT \leq PrV; PrT - PrV \leq 0$$

(*H_a*): The alternative hypothesis is that the probability of improving with drug T (*Pr_T*) is greater than to the probability of improving with vehicle (*Pr_V*).

$$H_a: PrT > PrV; PrT - PrV > 0$$

The change from baseline score of Skindex-16 will be compared among treatment at weeks 1, 4, 8 and 12 by a repeated measure analysis.

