10.1.2 Efficacy

Display Number	Title	Population	Unique/Repeat
14.2.1.1	Change from baseline in IGA score by Visit	mITT	Unique
14.2.1.2	Change from baseline in IGA score by Visit	PP	Repeat
14.2.2.1	Change from baseline in CEA score by Visit	mITT	Repeat
14.2.2.2	Change from baseline in CEA score by Visit	PP	Repeat
14.2.3.1	Change from baseline in PSA score by Visit	mITT	Repeat
14.2.3.2	Change from baseline in PSA score by Visit	PP	Repeat
14.2.4.1	Summary of Change from baseline in Skindex 16 score by Visit	mITT	Unique
14.2.4.2	Summary of Change from baseline in Skindex 16 score by Visit	PP	Repeat
14.2.5.1	Change from baseline in Telangiectasia score by Visit	mITT	Repeat
14.2.5.2	Change from baseline in Telangiectasia score by Visit	PP	Repeat
14.2.6.1	Summary of 2-grade improvement in IGA score from baseline to the end of treatment.	mITT	Unique
14.2.6.2	Summary of 2-grade improvement in IGA score from baseline to the end of treatment	PP	Repeat
14.2.7.1	Summary of 2-grade improvement in CEA score from baseline to the end of treatment	mITT	Repeat
14.2.7.2	Summary of 2-grade improvement in CEA score from baseline to the end of treatment .	PP	Repeat
14.2.8.1	Summary of IGA score of 0/1 at End of Treatment.	mITT	Unique
14.2.8.2	Summary of IGA score of 0/1 at End of Treatment.	PP	Repeat
14.2.9.1	Summary of CEA score of 0/1 at End of Treatment.	mITT	Repeat
14.2.9.2	Summary of CEA score of 0/1 at End of Treatment.	PP	Repeat
14.2.10.1	Summary of Sensitivity Analysis for Change from Baseline Score of IGA	mITT	Unique
14.2.10.2	Summary of Sensitivity Analysis for Change from Baseline Score of CEA	mITT	Repeat
14.2.10.3	Summary of Sensitivity Analysis for Change from Baseline Score of PSA	mITT	Repeat

Table 14.2.1.1
 Change from baseline in IGA Score by Visit.
 mITT Population

Visit	B244 Topical Spray N (xxx)	Placebo N (xxx)	All Patients N (xxx)
Week 1			
Change from Baseline			
1-grade	n (%)		
2-grade	n (%)		
3-grade	n (%)		
Repeat for all the visits			

CRF pages
 Source: <Dataset>
 Snapshot Data DD-MMM-YYYY
 Program Name: <Pgm name>

Repeat for CEA and PSA & Telangiectasia Score for mITT & PP population.

Table 14.2.4.1
 Summary of Change from baseline in Skindex 16 score by Visit
 mITT Population

Visit	B244 Topical Spray N (xxx)	Placebo N (xxx)	All Patients N (xxx)
Baseline			
N	xx	xx	xx
Mean (SD)	xx.x (xx.xxx)	xx.x (xx.xxx)	xx.x (xx.xxx)
CV	xx.x	xx.x	xx.x
Median	xx.x	xx.x	xx.x
Min, Max	xx.x, xx.x	xx.x, xx.x	xx.x, xx.x
Change from Baseline at Week 1			
N	xx	xx	xx

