Mean (SD)	xx.x (xx.xxx)	xx.x (xx.xxx)	xx.x (xx.xxx)
CV	xx.x	xx.x	xx.x
Median	xx.x	xx.x	xx.x
Min, Max	xx.x, xx.x	xx.x, xx.x	xx.x, xx.x

Repeat for All weeks

Final Analysis for Week 12	
Differences of LS Means	X.XXXX
SE	X.XXXX
CI	(X.XXXX, X.XXXX)
P-value	X.XXXX

SE: Standard Error of the LS Means

CRF pages

Snapshot Data DD-MMM-YYYY

Source: <Dataset>

Program Name: <Pgm name>

Repeat for PP population.

Table 14.2.10.1
 Summary of Sensitivity Analysis for Change from Baseline Score of IGA
 mITT Population

Imputation	B244 Topical Spray N (xxx)	Placebo N (xxx)	All Patients N (xxx)
Imputation#1			
N	xx	xx	xx
Mean (SD)	xx.x (xx.xxx)	xx.x (xx.xxx)	xx.x (xx.xxx)
Q1, Q3	xx.x, xx.x	xx.x, xx.x	xx.x, xx.x
Imputation#2			
N	xx	xx	xx
Mean (SD)	xx.x (xx.xxx)	xx.x (xx.xxx)	xx.x (xx.xxx)
Q1, Q3	xx.x, xx.x	xx.x, xx.x	xx.x, xx.x
Repeat for all imputations			
Analysis Summary			
Mean (SD)			x.xx, x.xx
CI			x.xxx
P-Value			

SD: Standard Error of the Parameters

CI: Confidence Interval

Repeat for CEA & PSA.

 CRF pages
 Source: <Dataset>

 Snapshot Data DD-MMM-YYYY
 Program Name: <Pgm name>

Table 14.2.6.1
 Summary of 2-grade improvement in IGA score from baseline to the end of treatment.
 mITT Population

	B244 Topical Spray N (xxx)	Placebo N (xxx)	All Patients N (xxx)
Subjects with 2-Grade improvement from Baseline to End of Treatment	n (%)	n (%)	n (%)
Risk Difference			x.xxx
CI			(x.xx, x.xx)
P-value			x.xxxx

CI: Confidence Interval

Source: <Dataset>

 Snapshot Data DD-MMM-YYYY
 Program Name: <Pgm name>

Repeat for PP Population and for CEA (mITT & PP).

Table 14.2.8.1
 Summary of IGA score of 0/1 at End of Treatment.
 mITT Population

	B244 Topical Spray N (xxx)	Placebo N (xxx)	All Patients N (xxx)
Subjects with Score of 0/1 at End of Treatment	n (%)	n (%)	n (%)
Risk Difference			x.xxx
CI			(x.xx, x.xx)
P-value			x.xxxx

CI: Confidence Interval

Snapshot Data DD-MMM-YYYY

Source: <Dataset>

Program Name: <Pgm name>

Repeat for PP Population and for CEA (mITT & PP)

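### The Week 12 Skindex-16 ANOVA names no baseline covariate, so it is less precise than an ANCOVA on data already collected; the size of the loss is uncertain and may be small

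*SAP*

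**What the plan says.** SAP v2.0, section 8.3, lists the endpoint as "Change of Skindex 16 patient reported outcome from Baseline to Week 1, Week 4, Week 8 and Week 12" and gives one inferential analysis for it: "The change from baseline score of Skindex-16 will be compared among treatments at Week 12 using an ANOVA". Weeks 1, 4 and 8 are descriptive. The v2.0 synopsis and SAP v1.0 describe the same test. The shell for Table 14.2.4.1 asks for "Differences of LS Means" with SE, CI and p-value at Week 12 and lists no model terms. Under SAP 6.4, "any statistical tests performed will use 2-sided tests at the 5% significance level" unless otherwise stated.

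The protocol differs. Its section 14.3.3 says that Skindex-16 change "will be compared among treatment at weeks 1, 4, 8 and 12 by a repeated measure analysis", also without naming a covariate.

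On data collection, Protocol 11.1.8 says "Skindex-16 instrument will be evaluated at each study visit", and the Schedule of Activities marks it at both Screening and Baseline.

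**The concern.** An ANOVA of change subtracts the whole baseline score, which amounts to fixing the slope of Week 12 on baseline at 1. If the true slope is below 1, this over-corrects. Subjects who start high tend to fall more whatever their treatment, so a chance difference between arms in baseline Skindex-16 passes into the treatment estimate. An ANCOVA estimates the slope instead.

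Nothing else in the plan offsets this. Randomisation is stratified by site only (Protocol 6.5). Eligibility limits IGA and CEA to 2-3 but sets no limit on Skindex-16. The multiple-imputation tables (14.2.10.1 to 14.2.10.3) cover IGA, CEA and PSA, not Skindex-16. At stake is an avoidably wide confidence interval for a Phase II estimate that may inform later planning.

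**Working it through.** **Inputs from the documents.** ANOVA of change at Week 12, two arms, 1:1, two-sided 5% level. SAP 8.1 gives 104 subjects, or 52 per arm. That number was set for IGA response (33% versus 10%), so it only provides a scale here. The plan has no Skindex-16 sample size, power, SD or correlation to reproduce.

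**Assumed inputs.** Within-arm correlation r between baseline and Week 12 of 0.3 to 0.7. Ratio k of the Week 12 SD to the baseline SD of 0.8, 1 and 1.25.

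**Formulas** (per-subject variance, baseline SD set to 1):

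- change score: k² + 1 − 2rk
- ANCOVA: k²(1 − r²)
- difference: (1 − rk)², which is never negative

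The treatment estimate from ANCOVA is the same whether the outcome is the change or the Week 12 score.

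**Equal SDs (k = 1).** The variances are 2(1 − r) and 1 − r², so the ratio is (1 + r)/2. For the power column, the effect is set so that the planned ANOVA has 80% power at 52 per arm.

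| r | Variance ratio | SE reduction | ANCOVA power | N giving the planned ANOVA's precision at 104 |
|---|---|---|---|---|
| 0.3 | 0.65 | 19.4% | 93.5% | 104 × 0.65 ≈ 68 |
| 0.5 | 0.75 | 13.4% | 89.9% | 104 × 0.75 = 78 |
| 0.7 | 0.85 | 7.8% | 86.0% | 104 × 0.85 ≈ 88 |

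A simulation of 4,000 trials per row gave variance ratios of 0.64, 0.74 and 0.86. Power rose from 79% to 93%, from 80% to 90% and from 80% to 86%.

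**Unequal SDs** (ratio of ANCOVA to change-score variance):

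| k | r = 0.3 | r = 0.5 | r = 0.7 |
|---|---|---|---|
| 0.8 | 0.50 | 0.57 | 0.63 |
| 1.25 | 0.78 | 0.89 | 0.98 |

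For k = 1.25 and r = 0.7, the change-score variance is 1.5625 + 1 − 1.75 = 0.8125 and the ANCOVA variance is 1.5625 × 0.51 = 0.797. The ratio is 0.98, so the SE falls by only about 1%. The cost of adjustment is one residual degree of freedom of 102.

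**Chance imbalance.** Given a baseline difference D between arms, the change-score estimate is shifted on average by −(1 − rk)D. The variance of that shift, per subject, is (1 − rk)², which is exactly the excess variance above. As an example with k = 1 and r = 0.5, D has SD √(2/52) = 0.196 baseline SDs. A one-SD imbalance then shifts the estimate by 0.5 × 0.196 = 0.098, half of the planned test's standard error of √(1 × 2/52) = 0.196.

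**The case against.** The main counter-argument is that a valid analysis of an exploratory, unsized endpoint is being criticised for efficiency alone, with a gain that rests wholly on assumed values. Much of this stands. The primary objective is safety, SAP 8.3 calls all efficacy endpoints exploratory, and the equal-SD figures can overstate the gain. A larger SD at Week 12 is plausible, because entry criteria narrow disease severity at baseline but not later. What does not follow is that the choice is neutral: within the model above, adjustment cannot lose precision beyond one degree of freedom.

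A reader might also infer several stronger things that the documents do not support:

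- *That the SAP fixes treatment as the only factor.* It says only that an ANOVA is used. The LS-means wording and the two PROC MIXED references do not establish a covariate, but silence does not exclude one either. The supportable statement is that none is named.
- *That this is the only between-arm patient-reported test.* In the 8.3 text, PSA change is descriptive: "Descriptive stats will be used to show the change from Baseline to Week 1, 4, 8 & 12". But the table list includes "Summary of Sensitivity Analysis for Change from Baseline Score of PSA", whose shell has a CI and p-value with the contrast undefined, and Protocol 14.3.3 counts PSA among the scores behind its superiority hypothesis.
- *That baseline information is discarded.* The change score uses it. Only the remaining precision is lost.
- *That Skindex-16 is stated to be completed before the first application.* The visit list places it earlier, but the explicit pre-application wording in the inclusion criteria covers CEA, IGA and the pregnancy test.

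It can also be said that adding a covariate leaves other Skindex-16 questions open. Protocol and SAP plan different analyses, and site, the stratification factor, appears in neither. That is fair. The covariate does not settle those points, but it is useful whichever way they are settled.

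**Conclusion.** The point holds as one of efficiency. The planned Week 12 test names no baseline covariate, and an ANCOVA would estimate the same treatment difference at least as precisely, apart from one degree of freedom. With equal SDs the variance is multiplied by 0.65 to 0.85 for r from 0.3 to 0.7. Allowing SD ratios of 0.8 to 1.25 widens the range to about 0.50 to 0.98. Both ranges rest on assumptions, since the documents give no Skindex-16 SD or correlation.

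The wider interval and the sensitivity to chance baseline imbalance are one loss described in two ways and should not be counted twice. A reader might take the imbalance term as evidence of bias or of an inflated type I error. It is neither: under randomisation the expected imbalance is zero, the change-score estimate is unbiased and the test keeps its level. Priority is low to moderate.

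**What to change.** In SAP 8.3 and the synopsis, replace the ANOVA with an ANCOVA of change from baseline, with treatment as factor and baseline Skindex-16 score as covariate. Use the same Baseline-visit value that is subtracted to form the change. State in the shell for Table 14.2.4.1 that the LS-mean difference, SE, CI and p-value come from this model.

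The Skindex-16 methods in SAP 8.3 and Protocol 14.3.3 must also be reconciled. If the repeated-measures analysis is used, include the same baseline covariate there. Whether to add site is a separate decision and is not quantified here.

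The cost is one line in two places, a table note and one model term. No new data are needed and no subject is lost. The change should be made before unblinding.
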